**9.1.2.2. Secondary aims.**

9.1.2.2.1. Secondary aim 1.

9.1.2.2.1.2. Aim.

Estimate and compare the per-lesion area under the ROC curve of a multivariate model that uses experimental as well as standard MRI features versus that of a model that uses only standard MRI features for the diagnosis of CRC metastases. Both models may use per-patient features such as age, gender, ethnicity, ascites, and anteroposterior diameter.

9.1.2.2.1.2. Analysis plan for secondary aim 1.

Using all available per-lesion MRI features (standard and experimental), per-subject MRI features (anteroposterior diameter and ascites), and per-subject clinical features (age, gender, ethnicity), multivariate models will be constructed to assess the discriminatory ability of each MRI feature after adjusting for the other features.

Other multivariate models will be constructed after excluding experimental features from consideration.

The area under the ROC curves corresponding to these models will be compared. To account for clustering due to multiple lesions for some patients and multiple observations per lesion, generalized estimating equation techniques will be used. The model with the largest area under the ROC curve will be identified.

9.1.2.2.2. Secondary aim 2.

9.1.2.2.1. Aim: Estimate the intraclass correlation coefficient of repeated quantitative measurements (T2\*, ADC, and shear modulus) on each lesion.

9.1.2.2.1.2. Analysis plan for secondary aim 2. The intra-class correlation coefficient between repeated measures will be calculated.

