#### **REQUIRED SAMPLE SIZE**

[figure not shown]
30 subjects will be enrolled in this pilot study.

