## **9.0 STATISTICAL CONSIDERATIONS**

### **9.1 Study Design and Endpoints**

#### **9.1.1. General study design.**

This is a prospective cohort pilot study assessing 3T MRI for diagnosis of CRC metastases to the liver in pre-hepatectomy patients. Consecutive eligible subjects with CRC metastases to the liver will undergo a research MRI of the liver within one week prior to curative hepatectomy done for clinical care. One radiologist will review the MR images and, for each focal lesion (benign or malignant) identified at imaging on each subject, assess 21 imaging features such as size, shape, margination, heterogeneity, kinetic enhancement pattern, and overall confidence for malignancy. Features will include binary, categorical, ordinal, and continuous variables. Sixteen features will be standard and five (T2\*, ADC, shear modulus, late venous phase signal intensity, and hepatocellular phase signal intensity) will be experimental. The MR sequences used to obtain the three quantitative experimental lesion features (T2\*, ADC, shear modulus) will be acquired twice for each subject. The radiologist also will assess two-per patient imaging features (abdominal AP diameter at the level of the portal vein bifurcation and the presence of ascites). Three demographic features (subject age, gender, ethnicity) will be available for the multivariate analyses; of the three, age will potentially be known to the radiologist as the scans will include the subject's date of birth.

For each subject, the lesions included in the analysis will be those identified at pre-hepatectomy imaging, *ex-vivo* imaging, pathology, or any combination of the three. The reference standard for each lesion will be the dichotomized histological diagnosis (malignancy versus other). Subjects are expected to have between one and ten CRC metastases in the hepatectomy specimen (average of three) and zero to five benign lesions (average of one). Subjects are not expected to have any malignancies other than CRC metastases.

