### **9.3 Sample Considerations**

With an accrual of 30 subjects, this study will provide a worst-case precision (i.e., confidence interval half width) of  $\pm 18\%$  at a sensitivity of 50% and 5% significance level. The precision will improve the larger the observed sensitivity is from 50%. Furthermore, the observed precision will be better than 18% because some subjects will have multiple lesions.

Assuming 75% of lesions are malignant, an average of four lesions per subject, and a moderate correlation (0.5) between measurements within subjects, this study will have 80% power at a significance level of 0.05 to detect an AUC of 0.7 or higher.

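### Secondary aim 1 compares AUCs of nested 26- and 21-predictor models in one 30-subject data set with no stated optimism correction, which favours the model with experimental features

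*Protocol*

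**What the plan says.** Protocol section 9.2, under the analysis plan for secondary aim 1, sets out three steps.

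- **Full models.** The candidate list opens "Using all available per-lesion MRI features (standard and experimental), per-subject MRI features (anteroposterior diameter and ascites" and continues with age, gender and ethnicity. The stated purpose is to judge each MRI feature adjusted for the others.
- **Reduced models.** Others are built with the experimental features left out of consideration.
- **Comparison.** The AUCs are compared, generalized estimating equations (GEE) account for clustering, and "The model with the largest area under the ROC curve will be identified".

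The expected data are given elsewhere. On size: "30 subjects will be enrolled in this pilot study". Section 9.1.1 expects each subject to have three CRC metastases on average. For the benign class, which is the smaller one, it expects "zero to five benign lesions (average of one") per subject. The abstract says that a future trial will assess the multivariate models further.

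**The concern.** The reduced pool is contained in the full pool, and the section describes one data set for both fitting and scoring. An AUC computed on the lesions that were used for fitting is too high, and the excess grows with the number of coefficients. The model with five more features therefore starts ahead even if those features are worthless. GEE changes standard errors to allow for several lesions per patient. It does not remove this excess: with an independence working correlation the point predictions are those of ordinary logistic regression.

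This is the protocol's only analysis of whether the experimental sequences add to the standard ones. If its answer leans one way by construction, the future trial would be planned on inflated AUCs and an unreliable ranking.

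**Working it through.** **The plan's own figure.** The protocol gives no power or precision for secondary aim 1. The nearest figure, in section 9.3, concerns one feature: "this study will have 80% power at a significance level of 0.05 to detect an AUC of 0.7 or higher". Its inputs are "Assuming 75% of lesions are malignant, an average of four lesions per subject", and "a moderate correlation (0.5) between measurements within subjects".

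- Lesions: 30 × 4 = 120, of which 0.75 × 120 = 90 are malignant and 30 benign.
- Design effect: 1 + (4 − 1) × 0.5 = 2.5, so the effective counts are 36 and 12.
- Hanley–McNeil terms at AUC 0.7: 0.7/1.3 = 0.5385 and 2 × 0.49/1.7 = 0.5765.
- Variance: [0.21 + 35 × (0.5385 − 0.49) + 11 × (0.5765 − 0.49)] / (36 × 12) = 0.0066, so SE = 0.081.
- Power: 0.2/0.081 = 2.46. One-sided 5%: Φ(2.46 − 1.645) = 79.2%. Two-sided 5%: Φ(2.46 − 1.96) = 69.1%.

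The 80% is reproduced one-sided, so these inputs are a fair base for the check.

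**Predictors against data.**

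- Full pool: 16 standard + 5 experimental lesion features + 2 per-patient imaging features + 3 demographic features = 26.
- Reduced pool: 26 − 5 = 21.
- Benign lesions per predictor: 30/26 = 1.2 (full) and 30/21 = 1.4 (reduced). With the design effect, 12/26 = 0.5 for the full pool.

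**Simulation with all features entered.** Assumptions: 30 subjects with 4 lesions each, about 30 benign; one parameter per feature; lesion features correlated 0.5 within subject; near-unpenalised logistic fits; all five experimental features pure noise. There were about 600 runs per row, new-data AUCs came from 1,000 further simulated subjects, and 10-fold cross-validation by subject was done in 200 runs. In each pair of AUCs the 21-predictor model comes first.

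| True AUC, standard features | AUC on fitting data | 26 higher | AUC in new data | 26 better in new data | Cross-validated AUC | 26 higher |
|---|---|---|---|---|---|---|
| 0.50 | 0.775 / 0.809 | 97.7% | 0.501 / 0.501 | 53% | 0.478 / 0.484 | 53% |
| 0.74 | 0.855 / 0.882 | 99.2% | 0.643 / 0.627 | 14% | 0.612 / 0.594 | 38% |
| 0.82 | 0.904 / 0.924 | 98.0% | 0.724 / 0.704 | 11% | 0.690 / 0.665 | 32% |
| 0.90 | 0.960 / 0.975 | 90.3% | 0.814 / 0.786 | 11% | 0.755 / 0.742 | 36% |

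The 21-predictor model was strictly higher on the fitting data in only 0.8 to 2.2% of runs; the rest were ties (8.5% in the last row). At true AUC 0.82 the apparent gain is 0.924 − 0.904 = +0.020, while the change in new data is 0.704 − 0.724 = −0.020. A separate simulation of the same design put the larger model ahead in 98% of runs at each of three signal levels. It was better in new patients in 11 to 19% of runs when there was signal, and ahead under subject-level cross-validation in 31 to 45%.

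**Simulation with forward selection** (true AUC 0.82, noise experimental features, 120 runs per rule).

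| Rule | Full pool higher | Tie | Full pool lower |
|---|---|---|---|
| AIC | 49% | 40% | 11% |
| p < 0.05 | 31% | 68% | 2% |

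**The case against.** **The fitting method is not settled by the text.** The protocol speaks of models in the plural, and of features left out of consideration, which can describe a candidate pool with selection. A reader might infer that the experimental model wins almost whatever the truth. That holds only if all features are entered. The reference to all available features, and to adjustment for the others, points that way without settling it. Under selection most of the remaining runs are ties, though wins still clearly outnumber losses.

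**The AUC is not called uncorrected.** That is so, and a separate analysis plan could add validation. But the protocol itself fixes the feature pools, the comparison and the largest-AUC sentence, and that sentence would still need rewording.

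**Identifying the largest AUC is not a claim of added value.** This stands. No rule turns a numerically larger AUC into a conclusion. In a similar simulation with nil to fairly strong standard signal, a cluster-adjusted two-sided 5% test of the AUC difference rejected in 11 to 14% of runs under noise. That is inflated but far from certain. Nor does the protocol say that only the model with the largest AUC goes forward.

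**Full dummy coding.** A reader might code every category in the feature table of section 6.11.3.3 and count 48 lesion parameters plus 5 patient parameters = 53, more than the 30 subjects. The protocol does not state that coding; it speaks of dichotomized and ordinal features. With 46 against 53 parameters, complete separation mostly yields ties once there is signal (41% wins and 59% ties with moderate signal). That shows fragile models rather than a near-certain win, so nothing here rests on that count.

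**It is a secondary aim of a pilot.** True. New patients in the future trial would expose the optimism. This lowers the severity but does not repair the comparison.

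**Conclusion.** The point holds in a limited form. As written, the comparison is tilted towards the model with experimental features. With all features entered and worthless experimental ones, the larger model shows the higher AUC in about 90 to 99% of runs, by about 0.015 to 0.034. It is better in new patients in only about 11 to 19% when the standard features carry signal. With forward selection the tilt shrinks to 31 to 49% wins against 2 to 11% losses, the rest ties.

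These figures assume the protocol's expected lesion counts and correlation, one parameter per feature, and AUCs computed on the fitting data, which is inferred from the silence on any correction. The documents do not support saying that the result is predetermined, or that the protocol would take a larger AUC as proof of added value. The primary aim is unaffected. This is a should-fix.

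**What to change.** In the analysis plan for secondary aim 1:

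- Base the comparison on AUCs corrected for optimism at subject level: leave-one-subject-out or grouped cross-validation, or a subject-level bootstrap. Any model building must be repeated inside each resample.
- Use the same lesions and the same patient covariates for both models, so that they differ only in the experimental features.
- Replace the largest-AUC sentence with the corrected AUC difference and its subject-level bootstrap interval.
- Optionally, penalise the fits or limit the number of predictors. Validation by subject already removes the built-in advantage in the simulation (larger model ahead in 32 to 53% of runs).

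The cost is some analysis work, with no added subjects or scans. Reported AUCs will be lower: at true AUC 0.82, 0.690 and 0.665 in place of 0.904 and 0.924. In that setting the cross-validated values also lie somewhat below the new-data values of 0.724 and 0.704.

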### **9.3 Sample Considerations**

With an accrual of 30 subjects, this study will provide a worst-case precision (i.e., confidence interval half width) of  $\pm 18\%$  at a sensitivity of 50% and 5% significance level. The precision will improve the larger the observed sensitivity is from 50%. Furthermore, the observed precision will be better than 18% because some subjects will have multiple lesions.

Assuming 75% of lesions are malignant, an average of four lesions per subject, and a moderate correlation (0.5) between measurements within subjects, this study will have 80% power at a significance level of 0.05 to detect an AUC of 0.7 or higher.

### **9.4 Randomization schema and stratification factors**

This is a cohort study. There will be no randomization or stratification of subjects.

### **9.5 Study monitoring, interim analyses, and early stopping rules**

Because this is a small pilot study with minimal risk, the PI will monitor the study for accrual and AEs. Every three months, the research coordinator will generate a summary report on accrual and participant demographics.

**10.0 Regulatory and Ethical Considerations**

**10.1 Protection of Patient Rights**

The PI, a liver radiologist, will monitor MR examinations and report any major, unexpected findings that may alter clinical management to the surgery team. The PI and the surgery team in consensus will formulate a list of findings to be reported. Patients will be informed of this possibility at the time of consent.

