**6.8. Research MRI (Visit 4)**

The research MRI will be done 2-10 days prior to the scheduled hepatectomy. The research coordinator and technologist will meet the subject upon arrival at the MR3T facility and confirm consent, re-review MR safety screening questionnaire, obtain a urine pregnancy test (if the subject is a woman of child bearing potential), and weigh the subject (to determine the appropriate contrast agent dose). The MRI examination will be performed (see Section 6.11). The PI or study investigator will monitor each MR examination and observe the subjects for adverse events until the subjects leave the MR facility. Adverse events will be recorded on an adverse event form (Section 8.0). Immediately prior to discharge from the MR facility, subjects will be given compensation as detailed in the consent form.

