**6.10. Criteria for Removal from Study**

Registered subjects will be withdrawn from the study if any of the following conditions are met:

- 6.10.1. Research MRI is not performed
- 6.10.2. Intravenous access cannot be established.
- 6.10.3. eGFR < 45 on blood sample drawn after registration
- 6.10.4. Subject has a positive urine pregnancy test after registration.
- 6.10.5. Hepatectomy is not performed.
- 6.10.6. Subjects withdraws his/her consent.
- 6.10.7. Exclusion criteria are discovered after registration but prior to MRI

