## 6.11. Imaging Acquisition, Archival, and Interpretation

### 6.11.1. Overview

Two MR examinations will be performed: a pre-hepatectomy MR examination on subjects (Section 6.11.2) and an *ex-vivo* MR examination on the resected specimen (Section 6.11.4). Both MR examinations will be performed on the same 3T research scanner. The only identifying information entered into the scanner will be the subject's study ID and date of birth. The study radiologist will analyze the pre-hepatectomy MRI only. The PI and other study investigators will use the combined information from the pre-hepatectomy MRI, *ex-vivo* MRI, and pathology specimen to define the surgical margin on the pre-hepatectomy images and to generate a lesion reference standard table (Section 6.13).

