### **6.11.3. Pre-hepatectomy MR imaging interpretation**

#### 6.11.3.1. Overview.

The study radiologist will have expertise in MRI of the liver. The radiologist will be trained on a test set to become familiar with the imaging criteria. After the training, the radiologist will review and interpret the pre-hepatectomy research exams. The radiologist will know the subject's study ID and date of birth, and will be aware that the subject has a pre-operative diagnosis of CRC metastasis to the liver. The coordinator will explain to the radiologist the segment(s) that were resected at surgery. The radiologist will be blinded to all other information. MR images (test set and research exams) will be reviewed on high-resolution >4 megapixel gray-scale monitors using the hospital PACS system.

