**6.12. Histology analysis**

Slides will be stained (haemotoxolin and eosin, trichrome, Prussian blue) at a histology lab. The study pathologist will review the slides and issue a dichotomous histological diagnosis for each submitted nodule (malignant or benign). Photographs of representative histology slides will be taken. One unstained slide will also be obtained as a precaution.

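### Selected research-MRI findings can reach the surgery team before hepatectomy, so the test under study can influence which lesions get histology, and no listed form records when it does

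*Protocol*

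**What the plan says.** **What may be passed on.** Under protocol section 10.1 the PI, a liver radiologist, monitors the MR examinations and will "report any major, unexpected findings that may alter clinical management to the surgery team". The scope is limited: "The PI and the surgery team in consensus will formulate a list of findings to be reported". The list is not given, so it is not known whether a new liver lesion would be on it.

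**Timing.** Section 6.8: "The research MRI will be done 2-10 days prior to the scheduled hepatectomy". The protocol does not state when a report is made, but one that arises from monitoring the scan can reach the surgeon before the operation.

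**Verification.** Nodules are located, sampled and diagnosed only in the hepatectomy specimen (6.11.4.1 and 6.12). Section 9.1.1 says that "the lesions included in the analysis will be those identified at pre-hepatectomy imaging", ex-vivo imaging or pathology, with histology as the reference standard. Section 6.10.5 withdraws a subject if "Hepatectomy is not performed".

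**The study read.** This is separate from the PI's monitoring. Section 6.11.3.1: "The coordinator will explain to the radiologist the segment(s) that were resected at surgery". The read therefore follows surgery and does not itself inform the surgeon.

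**What is recorded.** Under 6.11.1 the PI and other investigators combine the in-vivo MRI, the ex-vivo MRI and the specimen to "define the surgical margin on the pre-hepatectomy images". The data forms listed in 7.0.2 include no item for the resection planned before the MRI, for findings reported to the surgery team, or for a change or cancellation that follows.

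**The concern.** In an accuracy study the reference standard should be applied without regard to the index test result. Here a lesion outside the planned resection can enter the specimen because the MRI showed it and the PI reported it. A lesion outside the plan that the MRI missed cannot prompt a report and is less likely to be removed and examined. That is partial verification dependent on the index test, and it acts on the primary endpoint. If a report leads instead to cancelled surgery, the subject and all of that subject's lesions leave the analysis.

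The margin is drawn from the tissue actually removed, so it already contains any extension that the MRI prompted. Without a record of the plan made before the scan, the affected lesions cannot be identified reliably afterwards. A statistical analysis plan cannot repair that, because the information has to be captured before the MRI is viewed. The estimates are meant to support the planning of a larger trial (sections 1.0 and 2.0), and additional subjects would not remove a bias of this kind.

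**Working it through.** **1. The plan's own precision figure (9.3).** With 30 subjects at 50% sensitivity, the 95% half-width is 1.96 × √(0.5 × 0.5 / 30) = 0.179. The stated ±18% reproduces.

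**2. Inputs.**
- From the protocol: 30 subjects, with on average 3 metastases and 1 benign lesion each (4.0 and 9.1.1). This gives 30 × 3 = 90 malignant and 30 × 1 = 30 benign lesions, taken as lying inside the planned resection and all verified.
- From the protocol, as an illustration only: MR sensitivity 78%, the all-size figure quoted in section 2.0.
- Assumed, because the documents give no values: specificity (se and sp below are true sensitivity and specificity), M metastases and B benign lesions outside the plan, verified with probability v1 if MRI-positive and v0 if MRI-negative.

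**3. Wider resection.**
- Observed sensitivity = se(90 + M·v1) / [se(90 + M·v1) + (1 − se)(90 + M·v0)]
- Observed specificity = sp(30 + B·v0) / [sp(30 + B·v0) + (1 − sp)(30 + B·v1)]

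At se = 78% and sp = 80%:

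| M, B (per subject) | v1, v0 | Sensitivity | Specificity |
|---|---|---|---|
| 3, 3 (0.1, 0.1) | 1, 0 | 72.54/92.34 = 78.6% (+0.6) | 24/30.6 = 78.4% (−1.6) |
| 9, 6 (0.3, 0.2) | 1, 0 | 77.22/97.02 = 79.6% (+1.6) | 24/31.2 = 76.9% (−3.1) |
| 15, 15 (0.5, 0.5) | 1, 0 | 81.9/101.7 = 80.5% (+2.5) | 24/33 = 72.7% (−7.3) |
| 9, 6 | 1, 0.3 | 77.22/97.614 = 79.1% (+1.1) | 25.44/32.64 = 77.9% (−2.1) |
| any | 1, 1 | no shift | no shift |

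The same three pairs of M and B were combined with (v1, v0) of (0.5, 0), (1, 0) and (1, 0.3), and with (se, sp) of (78%, 80%), (50%, 80%) and (78%, 50%). The shifts run from +0.3 to +3.8 points in sensitivity and from −0.8 to −10.0 points in specificity. The extremes are 52.5/97.5 = 53.8% against 50% for sensitivity and 15/37.5 = 40% against 50% for specificity.

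**4. Cancelled surgery.** Assume 6 metastases in each withdrawn subject, of which MRI detects 95%. Starting from 90 × 0.78 = 70.2 detected of 90:
- 1 subject withdrawn: (70.2 − 5.7)/84 = 76.8% (−1.2)
- 2 withdrawn: (70.2 − 11.4)/78 = 75.4% (−2.6)
- 3 withdrawn: (70.2 − 17.1)/72 = 73.75% (−4.25)
- 1 withdrawn, plus 3 × 0.78 = 2.34 added MRI-positive metastases: (64.5 + 2.34)/(84 + 2.34) = 77.4% (−0.6)

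**5. A single feature.** The endpoint is per feature, not overall detection. If a feature is present in 60% of planned metastases but in 30% of added ones (assumed), then relative to the planned lesions:
- 3 added: (54 + 0.9)/93 = 59.0% (−1.0)
- 9 added: (54 + 2.7)/99 = 57.3% (−2.7)
- 15 added: (54 + 4.5)/105 = 55.7% (−4.3)

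**6. Against sampling error.** Every sensitivity shift above is well inside ±18 points. For specificity at 80% with 30 benign lesions, the half-width ignoring clustering is 1.96 × √(0.8 × 0.2 / 30) = 14.3 points, so a shift of −7.3 would be about half of it. No effect on AUC was calculated.

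**The case against.** **Limited scope.** Only important, unforeseen findings from an agreed list are reported. A reader might infer that the MRI read as a whole reaches the surgeon; 10.1 and 6.11.3.1 do not support that. This stands, and it narrows the route without closing it.

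**Direction.** A reader might infer that sensitivity is necessarily inflated and specificity deflated. That is the usual direction when test-positive lesions are preferentially verified, but cancellations and per-feature endpoints can pull sensitivity down, as steps 4 and 5 show. A wider resection also brings in neighbouring MRI-negative tissue. Section 2.0 notes that intra-operative ultrasound finds resectable metastases missed before surgery in about 20% of patients, although the protocol does not say that the study surgeon uses it. Either would raise v0 and shrink the shift. This objection stands.

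**Small metastases.** It is tempting to apply the model to sub-centimetre lesions, where the relative inflation would look large. No size-stratified endpoint is defined. Section 2.0 names MR before CT and then gives 12% and 23%, so the MR figure may be 12%. No such figure is relied on here.

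**Already limited to resected tissue.** Verification would be restricted to the specimen even without reporting. True; the added problem is that the restriction can depend on the test and goes unrecorded.

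**Records and later documents.** The surgeon sees patients four weeks before surgery (5.3), so clinical notes may show the plan, and the case report forms are pending (12.2). Notes are not a dependable substitute for a prospective entry, but pending forms make this an easy time to add one.

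**Conclusion.** The point holds in limited form. The protocol allows selected research-MRI findings to influence which tissue receives the reference standard, and also which subjects remain in the study, and its listed data forms do not capture this. The per-feature sensitivity, specificity and AUC can be biased as a result.

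Neither the net direction nor the size can be determined from the documents. The figures above rest on assumed counts of lesions outside the plan, assumed verification probabilities and assumed cancellations. Within those assumptions sensitivity moves by a few points either way, which is small beside the stated ±18%. Specificity is more exposed, because about 30 benign lesions carry it. If few reports change surgery, the effect is correspondingly small.

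The case for acting is that the information is cheap to collect beforehand and hard to recover later, and that it would allow the bias to be bounded. The documents do not support the stronger step of confining the primary analysis to lesions inside the planned resection: that would set aside verified lesions when benign ones are already few. The clinical reporting rule itself is not in question.

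**What to change.** Leave the reporting rule in 10.1 as it is, and make these changes:

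- **7.0.2:** add a field in which the surgeon records the planned resection before the research MRI is viewed. Add a log of each finding reported to the surgery team and any change to, or cancellation of, the operation that follows.
- **Lesion cross-reference table (6.11.4.1):** add a column that flags any lesion resected only because of such a report.
- **9.1.1 and 9.2:** keep the primary analysis on all verified lesions, and add a sensitivity analysis of sensitivity, specificity and AUC without the flagged lesions.
- **Reporting:** give the number of hepatectomies changed or cancelled after a report, with the lesion counts in those subjects.

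The cost is one form field, a short log, one table column and a small additional analysis. No lesion is lost from the primary analysis.
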